## 10 Safety monitoring and reporting

### 10.1 Definition of adverse events and reporting requirements

#### 10.1.1 Adverse events

An adverse event (AE) is any untoward medical occurrence (e.g., any unfavorable and unintended sign [including abnormal laboratory findings], symptom or disease) in a subject or clinical investigation subject after providing written informed consent for participation in the study. Therefore, an AE may or may not be temporally or causally associated with the use of a medicinal (investigational) product.

The investigator has the responsibility for managing the safety of individual subject and identifying adverse events.

Novartis qualified medical personnel will be readily available to advise on trial related medical questions or problems.

The occurrence of adverse events must be sought by non-directive questioning of the subject at each visit during the study. Adverse events also may be detected when they are volunteered by the subject during or between visits or through physical examination findings, laboratory test findings, or other assessments.

Adverse events must be recorded in the Adverse Events CRF under the signs, symptoms or diagnosis associated with them, accompanied by the following information (as far as possible) (if the event is serious refer to [Section 10.1.2](#)):

1. The Common Toxicity Criteria (CTC) AE grade (version 5.0 or higher). A copy of the CTCAE grading will be provided separately in the SOM.

Adverse events will be assessed and graded according to the Common Terminology Criteria for Adverse Events (CTCAE) version 5.0

2. its relationship to the study treatment and other investigational treatment. If the event is due to lack of efficacy or progression of underlying illness (i.e. progression of the study indication) the assessment of causality will usually be 'Not suspected'. The rationale for this guidance is that the symptoms of a lack of efficacy or progression of underlying illness are not caused by the trial drug, they happen in spite of its administration and/or both lack of efficacy and progression of underlying disease can only be evaluated meaningfully by an analysis of cohorts, not on a single subject
3. its duration (start and end dates) or if the event is ongoing, an outcome of not recovered/not resolved must be reported.
4. whether it constitutes a SAE (see [Section 10.1.2](#) for definition of SAE) and which seriousness criteria have been met

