### **12.5.2 Safety endpoints**

For all safety analyses, the safety set will be used. All listings and tables will be presented by treatment group.

Safety summaries (tables, figures) include only data from the on-treatment period with the exception of baseline data which will also be summarized where appropriate (e.g. change from baseline summaries). In addition, a separate summary for death including on treatment and post treatment deaths will be provided. In particular, summary tables for AEs will summarize only on-treatment events, with a start date during the on-treatment period (treatment-emergent AEs).

The on-treatment period lasts from the date of first administration of study treatment to 30 days after the date of the last actual administration of any study treatment.

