#### **Adverse events**

All information obtained on AEs will be displayed by treatment group and subject.

The number (and percentage) of subjects with treatment emergent AEs (events started after the first dose of study medication or events present prior to start of double-blind treatment but increased in severity based on preferred term) will be summarized in the following ways:

- by treatment, primary system organ class and preferred term;
- by treatment, primary system organ class, preferred term and maximum severity;
- by treatment, Standardized MedDRA Query (SMQ) and preferred term.

Separate summaries will be provided for study medication related AEs, death, SAEs, other significant AEs leading to discontinuation.

The incidence of psychotomimetic AEs will be tabulated by treatment group, according to severity and relationship to drug.

A subject with multiple AEs within a primary system organ class is only counted once towards the total of the primary system organ class.

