All information obtained on adverse events will be displayed by treatment group and subject.

Summary tables for AEs will summarize only on-treatment events, with a start date during the on-treatment period (treatment-emergent AEs). The on-treatment period lasts from the date of first administration of study treatment to 30 days after the date of the last actual administration of any study treatment.

The number and percentage of subjects with adverse events and drug-related adverse events will be separately tabulated, by body system and preferred term with a breakdown by treatment. A subject with multiple adverse events within a body system is only counted once towards the total of this body system and treatment.

In addition, the number and percentage of subjects with adverse events will be tabulated by body system, preferred term, maximum severity with a breakdown by treatment group. A subject with multiple severity ratings for an AE under treatment, is only counted under the maximum rating.

Summary tables to show the frequency of subjects affected, time (in hours) of onset and resolution time (in hours) by treatment (MIJ821 0.16 mg/kg pooled, MIJ821 0.32 mg/kg pooled and placebo) and total, will be provided for AEs of interest (dissociation, amnesia, dissociation and amnesia (together), sedation and vomiting).

For these summary tables of AEs of interest, the following guidelines will be applied:

1. Frequency / time to onset / time to resolution of AEs of interest:
 - Frequency - A subject with multiple AEs with the same preferred term (PT) is counted only once for that PT
 - Time to onset – A subject with multiple events in a preferred term of interest, we are only considering the first instant
 - Time to resolution – A subject with multiple events in a preferred term of interest, we are only considering the maximum of the AE duration

2. For subjects who experienced ‘Dissociation and amnesia’:
 - Time to onset – we will use time to 1st instant (whether it’s dissociation or amnesia)
 - Time to resolution – we will use maximum of the AE duration (whether it’s dissociation or amnesia)

3. Based on the consultation with the clinical team, the following rules for grouping of the AEs of interest were elicited:

AE of interest	Notes
Sedation	See AE grouping below
Dissociation	See AE grouping below + ‘dissociative amnesia’
Amnesia	Any term that includes ‘amnesia’, except for ‘dissociative amnesia’ which falls under ‘Dissociation’

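### Treatment-emergent AEs are selected by calendar start date, so a non-worsening AE that begins on Day 1 before the infusion is tabulated as treatment-emergent, against the Protocol's own after-first-dose definition

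*SAP*

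**What the plan says.** Two rules for treatment-emergence stand in the visible text.

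- **By calendar date.** SAP 7.1.1 (Adverse events) limits the AE summary tables to events "with a start date during the on-treatment period (treatment-emergent AEs"), and the period is defined by date: "The on-treatment period lasts from the date of first administration of study treatment". The opening of Protocol 12.5.2 has the same pair of statements: "summary tables for AEs will summarize only on-treatment events, with a start date during the on-treatment period", and "The on-treatment period lasts from the date of first administration of study treatment to 30 days after" the last administration. Neither place gives a clock time.
- **By onset relative to dosing.** The Adverse events paragraph of Protocol 12.5.2 defines treatment-emergent AEs as "events started after the first dose of study medication". A second limb of that definition admits "events present prior to start of double-blind treatment but increased in severity based on preferred term".

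On collection, Protocol 10.1.1 counts any untoward occurrence "after providing written informed consent for participation in the study" as an AE and asks for start and end dates. Section 3 allows the baseline evaluation on Day -1 or Day 1. Table 8-1 marks AE collection at baseline and at the Day 1 0h time point. Footnote 2 places 0h assessments before the infusion, and footnote 9 drops the repeat if both visits fall on one day.

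**The concern.** The date rule treats the whole of Day 1 as on-treatment, including the hours before any drug is given. The Protocol's definition does not. A programmer who follows the SAP literally will put a pre-infusion Day 1 event into the treatment-emergent tables, and from there into the registry tables, which are built on the same flag.

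The AE-of-interest table has an extra exposure. SAP 7.1.1 takes time to onset from the first instance of a preferred term. If a subject has the same event before and after the infusion on Day 1, the earlier one supplies the onset and the post-dose onset is lost. Several terms that the SAP groups under dissociation, such as feeling hot, tinnitus or blurred vision, are non-specific enough to occur before dosing.

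**Working it through.** No figure in the plan depends on this rule, so the check is to apply both rules to the same records. Assume, for illustration only, an infusion that starts at 10:00 on Day 1.

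| Record | Date rule (SAP 7.1.1; Protocol 12.5.2 opening) | Onset rule (Protocol 12.5.2, Adverse events) |
|---|---|---|
| 1. Starts 08:00 Day 1, does not worsen | Treatment-emergent | Not treatment-emergent |
| 2. Starts 08:00 Day 1, worsens after infusion | Treatment-emergent | Treatment-emergent |
| 3. Starts Day -1, worsens after infusion | Not treatment-emergent | Treatment-emergent |
| 4. Starts 11:00 Day 1 | Treatment-emergent | Treatment-emergent |

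Record 1 is the discrepancy at issue. Record 3 is a different one, in the opposite direction: the date rule has no worsening limb. It is not part of this point, though the same paragraph could be corrected for both.

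**Can record 1 arise?** Yes. AEs are recorded from consent. If baseline is on Day -1, the 0h assessment on Day 1 collects AEs before the infusion. If baseline is on Day 1, footnote 9 leaves that visit as the single pre-infusion collection. Either way there is one scheduled pre-infusion AE collection on Day 1.

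**Effect on time to onset.** Take one subject with the same preferred term at 08:00 and again at 11:00. The subject is counted once under either rule, because the 11:00 event qualifies by itself. Under the date rule the first instance is 08:00. Under the onset rule it is 11:00, which is 11 - 10 = 1 hour after the infusion began. The post-dose onset is what the table is meant to show.

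**Is finer timing already planned?** Yes, in three places in SAP 7.1.1. Onset and resolution of AEs of interest are reported in hours. Blood pressure change uses only measurements taken after the first injection. The interim AE outputs use a window of 48 hours from the first injection. The treatment-emergent rule alone stays at calendar-day level.

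**The case against.** The best defence is that the Protocol statements can be read together: the date rule sets a reporting window, and the Adverse events paragraph then decides which events inside it are treatment-emergent. The SAP says that it implements the Protocol's analysis, so the stricter definition would carry over. This does not hold, because both documents attach the treatment-emergent label directly to the date rule. A reader of the SAP has no second filter to apply.

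It is also fair to say that a date rule is a common, inclusive choice when clock times are not collected, and that Protocol 10.1.1 lists only start and end dates. That stands as a reason to keep an inclusive fallback for untimed events. It does not justify ignoring a time that has been recorded.

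Three stronger readings are tempting and are not supported:

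- **A reader might infer that the interim 48-hour outputs are contaminated.** That window is already anchored to the first injection, so a pre-infusion event falls outside it, and the interim listings name non-treatment-emergent events separately.
- **A reader might infer that the onset table will show negative hours.** That would follow only if hours are counted from the start of infusion, and the visible text does not state the origin.
- **A reader might infer bias between arms.** The events precede dosing in a randomised, blinded study, so they should not differ systematically by arm.

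**Conclusion.** The conflict is real and minor. The date rule in SAP 7.1.1 and in the opening of Protocol 12.5.2 classifies a non-worsening, pre-infusion Day 1 AE in the opposite way to the Adverse events paragraph of Protocol 12.5.2. It can also misstate onset in the AE-of-interest table.

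The documents give no rate of pre-infusion Day 1 events, so the number affected cannot be derived. It is probably small, being confined to part of one day per subject. The effect is a few background events spread over all groups of a non-confirmatory study with about 66 subjects.

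A reader might divide 66 by six arms to get 11 and conclude that each misclassified subject shifts an arm by 1/11, or about 9 percentage points. The documents do not support that figure: the allocation ratio is redacted, ketamine is given only in Europe, and the AE-of-interest table pools the MIJ821 regimens by dose.

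The conclusion rests on reading the visible rules as written. It assumes nothing about redacted text.

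**What to change.** In SAP 7.1.1 and Protocol 12.5.2:

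1. Start the on-treatment period at the date and time of the start of the first infusion.
2. For AEs with a Day 1 start date and a recorded start time, require onset at or after that time.
3. If the start time is missing, count the event as treatment-emergent unless it was recorded at the pre-infusion assessment (baseline or 0h).

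The 48-hour interim window needs no change.

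The cost is a wording edit in both documents; the Protocol edit needs a written amendment under Section 14.1. A start time for Day 1 AEs may have to be added to the AE form. The hours-based tables already need times for AEs of interest, but the visible text does not show that times are collected for all AEs. Slightly fewer events will be treatment-emergent.

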### **4.3 Rationale for choice of control drugs (comparator/placebo) or combination drugs**

The use of placebo saline solution is to provide a comparison group for an unbiased collection and assessment of safety and tolerability data.

Ketamine is included primarily for assay sensitivity and for comparison of side effects. Ketamine is known to be effective with large effect sizes for severe depressive episodes, and it also has high rates of dissociative side effects in 20-30% of subjects, often of moderate to marked severity. It also can cause manic episodes, mixed states, and suicidal or aggressive reactions in a small minority of persons. A single subanesthetic dose of intravenous ketamine consistently decreases symptoms of depression in subjects with treatment-resistant depression in a rapid (within hours), robust (across many symptoms of depression) and relatively sustained (typically, 7–14 days) manner ([Berman et al 2000](#); [Cusin et al 2017](#)). Repeated doses (six infusions over the course of several weeks) have shown promise from an efficacy and safety standpoint ([Aan het Rot et al 2010](#)). The efficacy of two times versus three times a week intravenous ketamine in subjects with treatment-resistant depression in sustaining the initial antidepressant effects was evaluated. Both doses (0.5 and 0.75 mg/kg) were significantly superior to placebo in treating depression symptoms and the transient dissociative side effects attenuated with repeat dosing ([Singh et al 2016](#)). One study examined the benefits of a fixed course of 4 once-weekly ketamine sessions (0.5 mg/kg IV) as continuation phase treatment in 5 patients who had remitted after acute phase treatment. All 5 patients maintained improvement during the continuation phase ([Krystal et al 1994](#)).

To limit any dissociative and psychomimetic side effects, the limiting dose for Ketamine infusion is at 40 mg/infusion for patients over 80 kg.

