1.4 Study design and treatment

This is a non-confirmatory, multi-center, 6-treatment arm in the European countries and 5-treatment arm in the USA (no ketamine arm), randomized, subject and investigator blinded, parallel group, placebo-controlled study in treatment-resistant depression patients. The study will randomize approximately 66 subjects and while the study design utilizes an outpatient visit schedule, the study allows for the inclusion of subjects seeking treatment for their disease from both an 'inpatient' or 'outpatient' clinic setting.

Subjects will be randomized to the following 6-treatment arms (USA will not include ketamine arm)

Commercially Confidential Information

Commercially Confidential Information

2 First interpretable results (FIR)

First interpretable results (FIR) will be provided for this trial.

Commercially Confidential Information

FIR will focus on the following analyses:

- Analysis populations (if needed)
- Subject disposition
- Demographics and baseline characteristics. Baseline characteristics include, but not limited to:
 - Body weight/height, BMI, age, sex, race, ethnicity, MADRS, Hamilton Anxiety Scale
- Safety results include but are not limited to:
 - Number and percentage of subjects with adverse events by body system and preferred term with a breakdown by treatment
 - Summary table presenting the frequency of subjects affected, time (in hours) of onset and resolution time (in hours) by treatment

Commercially Confidential Information

- Pharmacokinetic (PK) results for plasma (as appropriate, possibly using preliminary PK information with nominal collection times):

Commercially Confidential Information

- Efficacy/Pharmacodynamic (PD) analyses include, but are not limited to:

Commercially Confidential Information

3 Interim analyses

Commercially Confidential Information

4 Statistical methods: Analysis sets

Commercially Confidential Information

Commercially Confidential Information

5 Statistical methods for Pharmacokinetic (PK) parameters

All subjects within the PK analysis set will be included in the PK data analysis.

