Dissociation and Amnesia	Patients who experienced both amnesia and dissociation

	Applicant grouped:	We added:
Sedation	sedation; somnolence; altered state of consciousness; depressed level of consciousness; hypersomnia; stupor	loss of consciousness
Dissociation	dissociation; depersonalization/derealization disorder; derealization; dissociative disorder; flashback; hallucination; auditory hallucination; visual hallucination; illusion; somatic hallucination; hyperacusis; tinnitus; diplopia; vision blurred; ocular discomfort; photophobia; visual impairment; dysesthesia; oral dysesthesia; paresthesia; paresthesia oral; pharyngeal paresthesia; time perception altered; daydreaming; delusional perception; feeling hot; feeling cold; feeling of body temperature change	dysgeusia; dysmetropsia; feeling abnormal; feeling drunk; hyperesthesia; hypersensitivity; illusion; metamorphopsia; oral hyperesthesia; pharyngeal hypoesthesia; photopsia; photosensitivity reaction; synesthesia; altered visual depth perception; confusional state; delirium; hypogeusia; pain threshold decreased; hypoesthesia; eye hyperesthesia

Separate summaries will be provided for study medication related AEs, SAEs, other significant AEs leading to discontinuation.

In addition, a separate summary for death including on treatment and post treatment deaths will be provided.

For outputs of interim analyses, a safety window of adverse events occurring 48 hours after the 1st injection on Day 1, will be considered. All data for adverse events, as well as time of onset and resolution time for adverse events of interest, will be listed by treatment group and subject,

including non-treatment emergent adverse events and the treatment emergent adverse events occurring 48 hours after first injection on Day 1.

Relationship between dissociative, amnesia AE and MADRS total score

Commercially Confidential Information

ClinicalTrials.gov and EudraCT

For the legal requirements of ClinicalTrials.gov and EudraCT, two required tables on treatment emergent adverse events which are not serious adverse events with an incidence greater than 5% and on treatment emergent serious adverse events and SAE suspected to be related to study treatment will be provided by system organ class and preferred term on the safety set population.

If for a same patient, several consecutive AEs (irrespective of study treatment causality, seriousness and severity) occurred with the same SOC and PT:

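### The SAP's summary tables for adverse events of interest have no ketamine column, and their dissociation group counts hypersensitivity

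*SAP*

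**What the plan says.** SAP 7.1.1, under adverse events, plans tables of frequency, time to onset and time to resolution "by treatment (MIJ821 0.16 mg/kg pooled, MIJ821 0.32 mg/kg pooled and placebo) and total, will be provided for AEs of interest". The events are dissociation, amnesia, dissociation with amnesia, sedation and vomiting. The sentence is not redacted, and its list of columns looks complete.

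Protocol 12.5.2 sets the general layout for safety output: "All listings and tables will be presented by treatment group". On the ketamine arm, Protocol 4.3 states: "Ketamine is included primarily for assay sensitivity and for comparison of side effects". SAP 1.4 confirms that ketamine is a randomized arm in the European countries and is absent in the USA.

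The SAP then lists the preferred terms that make up each group. The dissociation list has a column of terms grouped by an applicant and a column of terms added. Hypersensitivity is in the second column. The SAP credits the grouping rules to consultation with the clinical team and gives no reason for individual terms.

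**The concern.** The secondary safety objective (Protocol Table 2-1) singles out dissociative side effects, and ketamine is the comparator against which they would be judged. Protocol 4.5 describes ketamine's psychotomimetic effects as mostly confined to administration and gone by 60 minutes afterward, with no impairment lasting more than 2 hours from the start of infusion. Onset and resolution are therefore natural points of comparison. The one visible summary that combines the SAP's grouped incidence with timing leaves out the comparator.

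The hypersensitivity entry raises a different problem. If the term carries the meaning it has in the protocol, an allergic or infusion reaction coded that way would be reported as dissociation, in whichever arm it occurred.

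**Working it through.** No sample-size or power figure is involved. The check compares texts and makes one count.

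**1. Columns against arms.** The design has 6 arms in Europe and 5 in the USA, and the difference is ketamine (SAP 1.4). The table columns cover MIJ821 at two pooled doses, and placebo. Ketamine is the only treatment named in the visible text that has no column.

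**2. What *total* can supply.** Its arms are not stated.
- If it includes ketamine, a reader could obtain the ketamine count as total − (0.16 mg/kg pooled + 0.32 mg/kg pooled + placebo). That would still not show its onset and resolution as a separate summary.
- If it excludes ketamine, it supplies nothing on ketamine.

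**3. What the other visible outputs supply for ketamine.**

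| Output | Ketamine kept? | SAP grouping? | Timing summary? |
|---|---|---|---|
| SAP 7.1.1 tables "by body system and preferred term with a breakdown by treatment", and the severity version | yes | no, single terms | no |
| Protocol 12.5.2 table by SMQ and preferred term | yes | a grouping, but by SMQ | no |
| Protocol 12.5.2: "The incidence of psychotomimetic AEs will be tabulated by treatment group, according to severity and relationship to drug" | yes | a grouping, terms not visibly defined | no |
| SAP 7.1.1: "All information obtained on adverse events will be displayed by treatment group and subject" | yes | can be derived by hand | no, a display |
| SAP 7.2.2 CADSS listing and MMRM; SAP 7.2.3 DES (largely redacted) | no exclusion visible | not applicable | not applicable |
| SAP section 2, first interpretable results: "Summary table presenting the frequency of subjects affected, time (in hours) of onset and resolution time (in hours) by treatment" | columns not named, next text redacted | not visible | yes, but for ketamine unknown |

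SAP 7.1.1 also plans a listing of onset and resolution times by treatment group and subject. It follows the sentence "For outputs of interim analyses, a safety window of adverse events occurring 48 hours after the 1st injection on Day 1, will be considered" and is a listing, not a summary.

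**4. Size of the dissociation group.** There are 28 terms in the applicant column and 20 in the added column. One (*illusion*) stands in both, and *dissociative amnesia* is brought in by the notes row. So 28 + 20 − 1 + 1 = 48 distinct terms.

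**5. Counting rule.** The SAP's frequency rule counts a subject once per preferred term. It does not say that a subject with several of the 48 terms counts once for the group, so group-level frequency is not fully defined for any arm.

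**6. Meaning of hypersensitivity.** Protocol 4.5 pairs it with infusion reaction and lists signs such as urticaria, bronchospasm and angioedema. Exclusion criterion 13 uses it for a history of reaction to study treatments, excipients or similar drugs. Section 9.1.1 gives anaphylaxis as an example. None of these uses is sensory. The sensory term *hyperesthesia* stands immediately before it in the SAP list.

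**The case against.** The strongest reply is that little is lost. Protocol 12.5.2 already plans two grouped incidence tables that keep ketamine, by SMQ and for psychotomimetic events. The dissociation objective also rests on CADSS and DES, where nothing visible excludes ketamine. An exact ketamine count under the SAP grouping could be worked out from the by-subject display once a group-level rule is fixed. Vomiting has no term list, so its ketamine frequency should be readable from the preferred-term table. The tables are a SAP addition that Protocol 12.5.2 does not itself require, and nearby SAP text is redacted.

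Most of this stands, and it sets the size of the point. A reader might infer that the plan abandons the side-effect comparison with ketamine, or that ketamine's grouped count cannot be recovered. The documents support neither reading. What survives is that the protocol's layout rule covers all safety tables without exception, the SAP gives no reason for departing from it, and a hand derivation from a display is not a planned summary. Redaction means only that the gap is in the visible text; it does not alter the stated columns.

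On hypersensitivity, the reply is that the clinical team chose the terms and that protocol prose does not settle what a coded term was meant to capture. That is fair, so the term should stay if a sensory meaning is documented. Subjects with relevant allergy or hypersensitivity histories are excluded (criteria 9 and 13), so cases may be few. A reader might infer that the dissociation rate is materially inflated; nothing in the documents shows that.

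**Conclusion.** The point holds as a minor descriptive correction. All 5 event categories lack a ketamine column. For dissociation, amnesia, their combination and sedation, the visible plan gives no ketamine incidence under the SAP grouping and no summary of timing. For vomiting, mainly the timing is missing. One of the 48 dissociation terms has, in the protocol's own usage, an allergic meaning.

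The number of ketamine cases left out cannot be estimated. Arm sizes are redacted, and the 20-30% rate in Protocol 4.3 concerns dissociative side effects, a narrower notion than the SAP group.

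The conclusion assumes that the column list is followed as written, that the Protocol 12.5.2 SMQ and psychotomimetic tables will be produced although the visible SAP 7.1.1 text does not repeat them, and that no redacted output already fills the gap. The study is non-confirmatory, and no inferential result changes.

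**What to change.** In SAP 7.1.1:

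- Add a descriptive ketamine column to the tables for adverse events of interest, with a footnote that ketamine was randomized only in Europe.
- State which arms *total* covers.
- State that a subject is counted once per group of interest, in addition to the existing rule per preferred term.
- Take hypersensitivity out of the dissociation group and report it under its own preferred term, unless the clinical team documents a sensory meaning. Delete the repeated *illusion* in the same edit.

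The cost is a change to table shells and the term list, plus one new sentence on counting. The same program can then be run with ketamine included. No new data are needed.
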